#### **5.4.1.3.2. Time to First HBsAg Seroconversion**

Time to first HBsAg seroconversion is defined as the number of days between the date of first study intervention intake and the date of the first occurrence of HBsAg seroclearance and appearance of anti-HBs antibodies (i.e. the date of the first HBsAg seroclearance and anti-HBs antibodies – the date of first study intervention intake + 1). The participants who withdrew early from the study before achieving HBsAg seroclearance and anti-HBs antibodies or who did not achieve HBsAg seroclearance and anti-HBs antibodies will be censored at the last available anti-HBs antibodies assessment.

Time to first HBsAg seroconversion will be the participants who were retreated with NA before achieving HBsAg seroclearance and anti-HBs antibodies will be censored at the date of NA retreatment.

#### **5.4.1.3.3. Time to HBV DNA < LLOQ**

Time to HBV DNA < LLOQ is defined as the number of days between HBV DNA >LLOQ for participants who re-treated with NA and the date of the first occurrence of HBV DNA < LLOQ after NA re-treatment (i.e. the date of the HBV DNA < LLOQ after being re-treated with NA – the date of first occurrence of HBV DNA>LLOQ + 1). Time to first HBV DNA < LLOQ will be analyzed only for participants who met the NA treatment completion criteria and re-treated with NA during FU.

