
 To explore HBV-specific T-cell responses during the study intervention and FU period.^b 	
 Changes from baseline in HBV-specific peripheral blood T-cell responses over time.^b

 To explore the efficacy of NA re-treatment in participants who meet the criteria for NA re-treatment. 	
 Proportion of participants who reach HBV DNA <LLOQ after re-start of NA treatment during the FU period.

 To explore medical resource utilization (MRU) to manage participants during study intervention and follow-up. 	
 Number and duration of medical care encounters, including surgeries, and other selected procedures (inpatient and outpatient) Duration of hospitalization (total days length of stay, including duration by wards; eg, intensive care unit) Number and character of diagnostic and therapeutic tests and procedures Outpatient medical encounters and treatments (including physician or emergency room visits, tests and procedures, and medications)

^a For the definition of virologic breakthrough, refer to Section 10.1, Appendix 1: Abbreviations and Definitions.

^b Peripheral blood mononuclear cell (PBMC) samples for immune analyses will be collected at selected sites only.

Refer to Section 8, Study Assessments and Procedures for evaluations related to endpoints.

For the definitions of terms, refer to Section 10.1, Appendix 1: Abbreviations and Definitions.

HYPOTHESIS

The primary hypothesis of this study is that at least one of the combination regimens of JNJ-3989+NA+PegIFN- α 2a is more efficacious than NA treatment alone (standard of care), as measured by the primary efficacy endpoint, the proportion of participants with a reduction of at least 2 log₁₀ IU/mL in HBsAg levels from baseline at Week 24. Because the study does not include a control arm, the hypothesis is formulated assuming a fixed external NA control response rate of 2% in terms of the primary efficacy endpoint.

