5.1. Inclusion Criteria

Each potential participant must satisfy all of the following criteria to be enrolled in the study:

A01 (adapted from M01) Adult male or female participants ≥ 18 (or the legal age of consent in the jurisdiction in which the study is taking place) to 65 years of age, inclusive.

M02 Participants must be medically stable based on physical examination, medical history, vital signs, and 12-lead ECG performed at screening. If there are abnormalities, they must be consistent with the underlying illness in the study population. This determination must be recorded in the participant's source documents and initialed by the investigator.

A03 (adapted from M03a) Participants must have chronic HBV infection. HBV infection must be documented by serum HBsAg positivity at screening. In addition, chronicity must be documented by any of the following, at least 6 months prior to screening: serum HBsAg positivity, HBeAg positivity or HBV DNA positivity, ALT elevation above ULN without another cause than HBV infection, documented transmission event. If none of the above are available, the following ways of documenting chronicity are acceptable at the time of screening: liver biopsy with changes consistent with chronic HBV, or absence of marker for acute HBV infection such as positive immunoglobulin M (IgM) anti-hepatitis B surface (HBs) and anti-HBc antibodies.

Participants should:

- be HBeAg-negative, AND
- be anti-HBe antibody-positive, AND
- be on stable HBV treatment, defined as currently receiving NA treatment for at least 2 years prior to screening, and having been on the same NA treatment regimen (at the same dose) as used in this study for at least 3 months at the time of screening, AND
- have documented serum HBV DNA < 60 IU/mL on 2 sequential measurements at least 6 months apart (one of which is at screening), AND
- have documented ALT values $< 2.0 \times$ ULN on 2 sequential measurements at least 6 months apart (one of which is at screening).

M04 Participants must have a body mass index (BMI; weight in kg divided by the square of height in meters) between 18.0 and 35.0 kg/m², extremes included.

A05 (adapted from M05)	Participants must sign a Master ICF (specific for the Master Protocol PLATFORMPAHPB2001) and must sign the ICF specific for this intervention cohort, indicating that he or she understands the purpose of, and procedures required for, the study and is willing to participate in the study.

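### Time to HBV DNA <LLOQ in re-treated participants is counted from the first HBV DNA >LLOQ, so it adds the wait before NA restart to the response after it

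*SAP*

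**What the plan says.** SAP 5.4.1.3.3 introduces the interval with "Time to HBV DNA < LLOQ is defined as the number of days between HBV DNA >LLOQ". In the formula the date subtracted is "the date of first occurrence of HBV DNA>LLOQ + 1". The event is "the date of the first occurrence of HBV DNA < LLOQ after NA re-treatment". The analysis "will be analyzed only for participants who met the NA treatment completion criteria and re-treated with NA during FU". The NA restart date therefore decides when an event may count, but it is not the time origin. The section does not confine the first value above LLOQ to the period after NA stop, and it does not say how to treat a re-treated participant who never falls below LLOQ.

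Other parts of the plan bear on this:

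- SAP 5.4.2.3 analyses all secondary time-to-event endpoints by Kaplan-Meier, with a log-rank test between arms.
- Protocol 6.5.2 has two HBV DNA criteria under which restart is to be considered: above 2,000 IU/mL with ALT above 5x ULN, and above 20,000 IU/mL. Each needs confirmation with 4 weeks or more between tests. Restart is immediate at more than 1,000,000 IU/mL or on signs of falling liver function.
- SAP Table 5 sets the HBV DNA LLOQ at 20 IU/mL. Under Protocol 5.1, criterion A03, participants must "have documented serum HBV DNA < 60 IU/mL on 2 sequential measurements at least 6 months apart".
- SAP 5.4.1.1.1 lets a participant stop NA with a Week 24 value below 60 IU/mL if the preceding visit was below LLOQ.

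**The concern.** The measured time has two parts: from first viraemia to NA restart, and from restart to suppression. Only the second describes response to NA. The first depends on which restart criterion was met and how long restart was deferred. Deferral is partly deliberate, because Protocol 4.2 warns that restarting too early may lower the chance of functional cure. It is also discretionary, because under the consider-restart criteria the decision is discussed with the sponsor.

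Two participants who re-suppress equally fast after restart can therefore have very different values. If the arms differ in how quickly viraemia returns or how soon sites restart NA, a log-rank difference could appear with no difference in response to NA, or a real difference could be masked.

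Two gaps in the wording add to this. With no earliest date, a programmer could start the clock on an on-treatment value just above LLOQ. With no censoring rule, re-treated participants who never suppress could be dropped or censored inconsistently.

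**Working it through.** The documents give no figure for this endpoint, so there is nothing to reproduce. The check applies the SAP formula to the target visit days and compares it with a clock started at restart.

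**Inputs.** Follow-up (FU) target days from SAP Table 4: FU Week 4 = 29, Week 8 = 57, Week 12 = 85, Week 20 = 141, Week 24 = 169, Week 36 = 253. From SAP Table 3, FU Day 1 is the date of Week 24 dosing, that is treatment-period Day 169 on target; FU Day d is then treatment-period Day 169 + d − 1. The participant paths are assumptions chosen for illustration.

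**Formulas.**
- SAP time = (date of <LLOQ after restart) − (date of first >LLOQ) + 1
- Restart-based time = (date of <LLOQ after restart) − (date of NA restart) + 1
- Difference = (date of NA restart) − (date of first >LLOQ)

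**Paths with the clock starting off treatment.**

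| Path | First >LLOQ | Restart | <LLOQ | SAP time | From restart | Before restart |
|---|---|---|---|---|---|---|
| A: low first value, >20,000 at FU W8, confirmed FU W12 | FU W4 | FU W12 | FU W24 | 169 − 29 + 1 = 141 | 169 − 85 + 1 = 85 | 56 (40%) |
| B: first value already >20,000, confirmed FU W12 | FU W8 | FU W12 | FU W24 | 169 − 57 + 1 = 113 | 85 | 28 (25%) |
| E: longer deferral | FU W4 | FU W24 | FU W36 | 253 − 29 + 1 = 225 | 253 − 169 + 1 = 85 | 140 (62%) |
| D: first value >1,000,000, same-visit restart | FU W8 | FU W8 | FU W20 | 141 − 57 + 1 = 85 | 85 | 0 |

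**Minimum wait.** Where the HBV DNA criterion is confirmed 4 weeks apart, the first value above LLOQ falls on or before the first qualifying value, so the wait is at least 4 × 7 = 28 days. Protocol 4.2 allows exceptions to the 4-week gap (earlier re-testing at high HBV DNA or ALT values), so the minimum applies only where that gap was observed.

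**Paths on the literal reading of first occurrence.** Each continues as path A.
- Week 24 value above 20 and below 60 IU/mL: 169 − 1 + 1 = 169 days, of which 84 (50%) precede restart.
- Day 1 value in the same range: FU Day 169 is treatment-period Day 169 + 169 − 1 = 337, so 337 − 1 + 1 = 337 days, of which 252 (75%) precede restart.

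**Censoring compared.** For participants without the event, censoring at the last relevant assessment is stated for HBsAg seroclearance (5.4.1.3.1), seroconversion (5.4.1.3.2), virologic breakthrough (5.4.1.3.4) and flares (5.4.1.3.5). Section 5.4.1.3.3 has no such sentence.

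**The case against.** The strongest reply is that the section never claims to measure speed of response to NA. The plan lists time to HBV DNA <LLOQ under the general blood-marker objective. The objective on re-treatment, "To explore the efficacy of NA re-treatment in participants who meet the criteria for NA re-treatment", is exploratory and has its own endpoint: the share reaching <LLOQ after restart, which SAP 5.4.2.1.10 summarises by arm with a 90% CI. From first viraemia to re-suppression is also a coherent quantity, the duration of a viraemic episode, and for that quantity the untreated wait belongs in the measure.

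Much of this stands. A reader might infer that the plan cannot assess NA re-treatment at all; the restart-based proportion shows otherwise. What remains is that the section does not call the measure a duration of viraemia, yet restricts it to re-treated participants and ties the event to restart. No other endpoint gives a time from restart.

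A reader might also infer that the clock will start at baseline. The text permits it, but those analysed qualified to stop NA at a suppressed or nearly suppressed level, so the rise after stopping was probably meant. This is a risk of literal programming, and the documents do not say how many participants it could touch.

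Nor is this the only time-to-event definition without explicit censoring at the last assessment: the additional HBsAg thresholds and declines in 5.4.1.3.1 lack it too. That does not supply the missing rule here.

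**Conclusion.** The point holds as a defect of definition. The measured time is the wait before restart plus the response after it, and the first part cannot contain an event. Results by arm would partly reflect restart timing. In the off-treatment paths the wait ranges from 0 to 140 days against a fixed 85-day response. These paths are illustrative; the documents give no frequencies for them, so the size of any distortion between arms is unknown.

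The missing lower bound and the missing censoring rule are secondary gaps in wording. The reach is limited: one secondary summary, without multiplicity adjustment, in a small subset formed after randomisation. The primary endpoint and the proportion suppressed after restart are unaffected.

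**What to change.** In SAP 5.4.1.3.3, define the time as the date of first HBV DNA <LLOQ after NA restart, minus the date of NA restart, plus 1, in re-treated participants with HBV DNA at or above LLOQ at restart. Censor those who do not reach <LLOQ at their last available HBV DNA assessment.

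If duration of viraemia is also of interest, report it as a separate endpoint under that name, starting at the first HBV DNA at or above LLOQ after NA stop.

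The cost is two sentences in the SAP, plus one more if the second endpoint is kept. No new data are needed: the restart date is on the NA drug administration CRF page named in SAP 5.4.1.1.2, and SAP 5.4.1.3.1 and 5.4.1.3.2 already use it as a censoring date.

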#### **5.4.1.3.4. Time to First Virologic Breakthrough**

Time to first HBV virologic breakthrough will be defined as the number of days between the date of first study intervention intake and the date of the first occurrence of virologic breakthrough (i.e. the date of the first virologic breakthrough [the first of the two confirmation visits] - the date of first study intervention intake +1). The participants who withdrew early from the study before experiencing virologic breakthrough or who did not experience virologic breakthrough will be censored at the last available HBV DNA assessment at or before EOT.

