6.5.1. NA Treatment Completion

All participants will receive the last dose of JNJ-3989 at Week 24 and the last dose of PegIFN- α 2a at Week 23 (Arms 1 and 2) or Week 11 (Arm 3). They will start the FU Period after the Week 24 visit. If all of the following NA treatment completion criteria are met based on the Week 24 results, treatment with NA will be stopped at the next scheduled visit (ie, FU Week 2):

- The participant has ALT <3x ULN, AND
- The participant has HBV DNA <60 IU/mL at Week 24 and HBV DNA <LLOQ at the previous visit, or HBV DNA <LLOQ at Week 24, AND
- The participant is HBeAg-negative, AND
- The participant has HBsAg <100 IU/mL.

Note: Participants who are close to meeting the protocol-defined NA treatment completion criteria with the Week 24 results, and do meet the criteria based on the FU Week 2 results may be allowed to stop NA at FU Week 4, after consultation with the Sponsor. In case of ALT elevation \geq 3x ULN at Week 24, the investigator must consider different potential causes of increased ALT to ensure appropriate work up and management as needed. If the ALT elevation is unrelated to HBV activity and/or <3x ULN by FU Week 2, NA completion may be considered at the discretion of the investigator and in consultation with the sponsor.

Participants who do not meet the above criteria based on the Week 24 or FU Week 2 results should continue NA treatment during the 48-week FU Period.

Participants who meet the above-mentioned NA treatment completion criteria will be monitored closely during the 48-week FU Period with a study visit at least once every 4 weeks. NA treatment should be re-started in accordance with the NA re-treatment criteria (see Section [6.5.2](#), NA Re-treatment Criteria During Follow-up, for more details).

The investigator should consider to re-start NA treatment per local standard of care at the EOS visit (Follow-up Week 48) for participants who met the NA treatment completion criteria based on the Week 24 (or FU Week 2) results, who did not re-start NA treatment during the follow-up phase, and who did not achieve and maintain HBsAg seroclearance. NA will not be provided by the sponsor after the final study visit.

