Week 2), otherwise NA treatment will continue during the complete FU period. Note: Participants who are close to meeting the protocol-defined NA treatment completion criteria with the Week 24 results, and do meet the criteria at FU Week 2 results may be allowed to stop NA at FU Week 4, upon prior discussion with the Sponsor.

The NA treatment completion criteria which take ALT, HBV DNA, HBeAg, and HBsAg levels into consideration, have been selected to ensure that only participants with a higher chance of achieving sustained off-treatment response are allowed to stop all study intervention. Participants who meet the protocol-defined NA treatment completion criteria will be monitored closely during the 48-week FU Period and participants should re-start NA treatment if NA re-treatment criteria are met (see Clinical Protocol Section 6.5.2, NA Re-treatment Criteria During Follow-up, for more details).

If a participant prematurely discontinues JNJ-3989 (ie, before Week 24), the participant will have an early WD visit and will enter the 48-week follow-up period as per the Schedule of Activities, unless the participant withdraws consent.

If a participant prematurely discontinues PegIFN- $\alpha$ 2a (ie, before Week 23 [Arms 1 and 2] or before Week 11 [Arm 3]), treatment with JNJ-3989 and NA should be continued as planned.

If a participant withdraws prematurely from the study, the reason for withdrawal (if known) should be documented in the case report form (CRF) and in the source document. Participants who withdraw consent will be offered an optional safety follow-up visit to occur on the day of consent withdrawal.

An internal Data Review Committee (DRC) will be commissioned for monitoring safety of participants enrolled in this study. In addition, an Independent Flare Expert Panel (IFLEP) will be appointed.

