**Table 4: Visit Windows**

Analysis phase	Target Day	Analysis time point (Week)	Analysis time point (label)	Time interval (days)
Screening	$-\infty$	-1	Screening	<0
Treatment period	1	0	Baseline	Pre-dose: 1
	15	2	Week 2	[2, 22]
	29	4	Week 4	[23, 43]
	57	8	Week 8	[44, 71]
	85	12	Week 12	[72, 92]
	99	14	Week 14	[93, 106]
	113	16	Week 16	[107, 127]
	141	20	Week 20	[128, 155]
	169	24	Week 24	[156, 183]
		Last visit in treatment period	25 a	EOT a
Follow-up	15	26	Follow-up Week 2	[1, 22]
	29	28	Follow-up Week 4	[23, 43]
	57	32	Follow-up Week 8	[44, 71]
	85	36	Follow-up Week 12	[72, 99]
	113	40	Follow-up Week 16	[100, 127]
	141	44	Follow-up Week 20	[128, 155]
	169	48	Follow-up Week 24	[156, 183]
	197	52	Follow-up Week 28	[184, 211]
	225	56	Follow-up Week 32	[212, 239]
	253	60	Follow-up Week 36	[240, 267]
	281	64	Follow-up Week 40	[268, 295]
	309	68	Follow-up Week 44	[296, 323]
	337	72	Follow-up Week 48	[324, $+\infty$ ]
	Last visit in the study	999 b	EOS b	

a End of treatment (EOT) visit will be the last post-baseline visit in treatment period.

b End of study (EOS) visit (last available data during the follow-up visit) will be the last visit in the study.

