#### **5.4.1.1.13. Virologic Breakthrough**

HBV virological breakthrough is defined as having a confirmed on-treatment HBV DNA increase by  $>1 \log_{10}$  from nadir level (lowest level reached during treatment) in participants who didn't have on-treatment HBV DNA level below the lower limit of quantification (LLOQ) or a confirmed on-treatment HBV DNA level  $>200$  IU/mL in participants who had on-treatment HBV DNA level below the lower limit of quantification (LLOQ). Confirmed HBV DNA increase/level means that the criterion should be fulfilled at 2 or more consecutive time points or at the last observed time points or at the last observed on-treatment time point. On-treatment will be defined as the time period in which the participant receives any of the study interventions (including NA).

In addition, participants who experience a virologic breakthrough followed by on-treatment biochemical flare will be evaluated.

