#### **5.4.1.1.14. Flares**

The criteria based on blood markers/lab tests for each of the flare types are defined as below.

**1. Virologic flare** is defined as follows:

Virologic flare will be assessed only for those participants who are off-treatment.

The start of a confirmed virologic flare is defined as the first date of two consecutive visits with HBV DNA  $>200$  IU/mL. The end date of the same confirmed virologic flare is defined as the first date when HBV DNA value returns to  $\leq 200$  IU/mL or the date of NA treatment restart, whichever

comes first. Each virologic flare will be categorized based on the confirmed (i.e. two consecutive values) peak HBV DNA above any of the three thresholds within the start and end date of that flare as follows: 20,000 IU/mL 2,000 IU/mL and 200 IU/mL.

- 1 (Yes) = confirmed\*\* HBV DNA > peak threshold.
- 0 (No) = at least one off-treatment HBV DNA measurement available and not meeting the criteria of confirmed HBV DNA > peak threshold.
- 2 (Not applicable) = no off-treatment HBV DNA quantitative measurements available.

**2. Off-treatment Biochemical flare** is defined as follows:

The start date of a confirmed off-treatment biochemical flare is defined as the first date of two consecutive visits with ALT and/or AST  $\geq 3x$  ULN and  $\geq 3x$  off-treatment nadir (i.e. lowest value observed during off-treatment period up to the time point of meeting the biochemical flare criteria) while the participant does not receive any of the study interventions. The end date of the same off-treatment biochemical flare is defined as the first date when there is a 50% reduction from the peak ALT and/or AST level &  $< 3x$  ULN.

- 1 (Yes) = confirmed\*\* ALT and/or AST  $\geq 3x$  ULN and  $\geq 3x$  nadir (i.e. lowest value observed up to the start of the flare)
- 0 (No) = otherwise

**3. On-treatment Biochemical flare** is defined as follows:

The start date of a confirmed on-treatment biochemical flare is defined as the first date of two consecutive visits with ALT and/or AST  $\geq 3x$  ULN and  $\geq 3x$  on-treatment nadir (i.e. lowest value observed on-treatment period up to the time point of meeting the biochemical flare criteria) while the participant receives any of the study interventions. The end date of the same on-treatment biochemical flare is defined as the first date when there is a 50% reduction from the peak ALT and/or AST level &  $< 3x$  ULN, regardless of stopping the study interventions.

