- 1 (Yes) = confirmed\*\* ALT and/or AST  $\geq 3x$  ULN and  $\geq 3x$  nadir (i.e. lowest value observed up to the start of the flare)
- 0 (No) = otherwise

**4. Clinical flare** is defined as follows:

A clinical flare occurs either when a virologic flare and biochemical flare overlap in time or when a biochemical flare starts within 4 weeks following the end of a virologic flare. The start date of a clinical flare is defined as the minimum start date of the virologic flare and the biochemical flare. The end date of a clinical flare is defined as the maximum end date of the virologic flare and biochemical flare, i.e., the later date of HBV DNA returns to  $\leq 200$  IU/mL and 50% reduction from the peak ALT and/or AST level.

- 1 (Yes) = confirmed\*\* HBV DNA > peak threshold and confirmed\*\* ALT and/or AST  $\geq 3x$  ULN and confirmed\*\*  $\geq 3x$  nadir (i.e. lowest value during study participation).

- 0 (No) = otherwise

\*\* Confirmed means that the criterion should be fulfilled at 2 or more consecutive time points or at the last observed time point.

The virologic and clinical flares will be assessed only off-treatment, while biochemical flares will be identified on-treatment and off-treatment. On-treatment virologic flares are described as virologic breakthrough in Section 5.4.1.1.13. On-treatment will be defined as the time period in which the participant receives any of the study interventions. Off-treatment will be defined as the period after stopping all study interventions (including NA).

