#### **5.4.1.3.5. Time to First Flare**

Time to first biochemical flare (on- and off-treatment), clinical flare off-treatment, and virologic flare off-treatment will be evaluated.

Time to first on-treatment flare will be defined as the number of days between the date of first study intervention intake and the date of the first occurrence of on-treatment flare (i.e. the date of the first on-treatment flare [the first of the two confirmation visits] of each type- the date of first study intervention intake+1). The participants who withdrew early from the study before experiencing on-treatment flare or who did not experience on-treatment flare will be censored at the last available blood markers or liver enzymes assessment at or before EOT.

Time to the first off-treatment flare will be defined as the number of days between the date of last study intervention intake and the date of the first occurrence of off-treatment flare (i.e. the date of experiencing the first off-treatment flare [the first of the two confirmation visits] of each type- the date of last study intervention intake). The participants who withdrew early from the study before experiencing off-treatment flare or who did not experience off-treatment flare will be censored at the last available blood markers or liver enzymes assessment.

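### Time to first virologic breakthrough and time to first on-treatment flare count events during follow-up on NA but censor everyone else by about Week 24, so a late event can take the Kaplan-Meier curve to 100%

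*SAP*

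**What the plan says.** Five rules bear on this point.

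- **What counts as an event.** For breakthrough, SAP 5.4.1.1.13 states: "On-treatment will be defined as the time period in which the participant receives any of the study interventions (including NA"). For on-treatment biochemical flare, SAP 5.4.1.1.14 requires the criteria to be met "while the participant receives any of the study interventions". The other side of the boundary is set there too: "Off-treatment will be defined as the period after stopping all study interventions (including NA").
- **How long NA lasts.** NA stops at FU Week 2 if the completion criteria are met on the Week 24 results; the SAP note to Figure 1 adds "otherwise NA treatment will continue during the complete FU period". Protocol 6.5.1 agrees: participants who miss the criteria "should continue NA treatment during the 48-week FU Period".
- **When event-free participants are censored.** For breakthrough (SAP 5.4.1.3.4), those who "did not experience virologic breakthrough will be censored at the last available HBV DNA assessment at or before EOT". For flares (SAP 5.4.1.3.5), those who "did not experience on-treatment flare will be censored at the last available blood markers or liver enzymes assessment at or before EOT".
- **What EOT is.** Table 4 of the SAP: "End of treatment (EOT) visit will be the last post-baseline visit in treatment period". Table 3 ends that period at about Week 24, or earlier for someone who discontinues early.
- **The estimator.** SAP 5.4.2.3 prescribes Kaplan-Meier cumulative incidence per arm, medians with 90% CIs and log-rank tests. Both clocks start at first intake.

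The off-treatment flare endpoint, also in SAP 5.4.1.3.5, has no EOT cap on its censoring.

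**The concern.** The event window can run to FU Week 48, while the censoring window closes at about Week 24. Once the last EOT date in an arm has passed, the only people left in the risk set are those who will later have an event. Kaplan-Meier assumes that the people still at risk represent those already censored. Here they are selected because they fail.

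Triggering events are plausible. Anyone who misses the completion criteria is on NA throughout follow-up. A participant who stops and then restarts NA is on-treatment again by the SAP's definition, and restart is tied to raised HBV DNA (Protocol 6.5.2). Two consecutive values above 200 IU/mL soon after restart, in someone with an earlier on-treatment value below LLOQ, would literally meet the breakthrough definition.

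At stake is a published curve and median that show an infrequent event as certain, in whichever arm it happens to fall. The alternative is a programmer choosing an unstated rule once open-label data are visible.

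**Working it through.** The documents give no figure for these endpoints, so there is none to reproduce. The check applies the SAP's rules literally to one arm.

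**Inputs.** Arm size 34 (SAP 3). EOT at Day 169, the Week 24 target day (SAP Table 4). Follow-up days from first intake: FU Week 2 = 169 + 14 = 183; FU Week 12 = 169 + 84 = 253; FU Week 24 = 169 + 168 = 337; FU Week 48 = 169 + 336 = 505. At each event time, S is multiplied by (1 − d/n), where d is the number of events and n the number at risk. Cumulative incidence is 1 − S.

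**As written, one follow-up event.** 33 participants are censored at Day 169 and one has an event at Day 253. Then n = 1, d = 1, S = 1 × (1 − 1/1) = 0, so cumulative incidence goes from 0% to 100% and the median is Day 253. The result is the same for an event at Day 183, 337 or 505, with EOT visits spread over the ±3-day window and an FU Week 2 event, and with all 102 participants pooled. The crude proportion is 1/34 = 2.9%.

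**As written, several events.**
- Two follow-up events: 1 − 1/2 = 50%, then 100%.
- One event at Day 85 and three in follow-up: 1/34 = 2.9%; 1 − (33/34)(2/3) = 35.3%; 1 − (33/34)(2/3)(1/2) = 67.6%; then 100%.

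The last follow-up event always takes the curve to 100%.

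**With matched windows, one event at Day 253.**
- Events limited to EOT: no event is counted, so 0%.
- Follow-up events kept, with others censored at their last on-NA assessment. If m of the 33 others are still on NA and observed at Day 253, the estimate is 1/(m + 1). The rest are assumed to stop NA at FU Week 2.

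| m still on NA | Cumulative incidence |
|---|---|
| 33 | 1/34 = 2.9% |
| 25 | 1/26 = 3.8% |
| 17 | 1/18 = 5.6% |
| 10 | 1/11 = 9.1% |
| 5 | 1/6 = 16.7% |

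The documents do not give m, so these rows are assumptions.

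**When the distortion does not arise.** EOT is specific to each participant. Suppose an early discontinuer who stays on NA has an event at Day 120, one other participant was censored at Day 57, and 32 are still before EOT. Then n = 33 and the estimate is 1/33 = 3.0%.

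**Log-rank test.** With one follow-up event and nobody else at risk in any arm, observed is 1, expected is 1/1 = 1, O − E = 0 and the variance is 0. The event adds nothing to the comparison.

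**The case against.** The strongest reply is that a workable reading exists. SAP 5.4.2 presents summaries and graphs by arm and analysis phase unless stated otherwise, and SAP 5.4.1.2.1 equates the on-treatment nadir with the first 24 weeks. With an explicit EOT cap on censoring, the author may have meant a treatment-period curve with follow-up events outside it. That may be the intent, and it is the simplest repair, but the text does not say it. Neither time-to-event section limits events to the treatment period, the definition of on-treatment expressly includes NA, the breakthrough objective covers the whole study, and SAP 5.4.2.3 specifies curves by arm. A display rule does not restrict which events count. Nor can EOT be read as the end of NA: SAP 5.1.6 refers to participants who met the completion criteria at EOT, which precedes any planned NA stop.

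The second reply concerns consequence, and it largely stands. SAP 5.4.2.1.13 and 5.4.2.1.14 report proportions and incidence without EOT censoring. SAP 5.1.5 requires the Kaplan-Meier table to show the number censored, so a careful reader would see 33 of 34. Table 10 sends breakthrough and flares to the DRC at every review. Protocol section 3 lists the proportion with breakthrough and the frequency of flares as endpoints; the time-to-event versions are SAP additions with no multiplicity-controlled test.

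A reader might also infer that the log-rank tests become invalid as soon as one on-NA event occurs in follow-up. The arithmetic does not support that. A lone late event is discarded, and the test equals the treatment-period test. Only when participants from more than one arm remain in the late risk set can such events add anything.

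**Conclusion.** The two endpoints are wrong as written: events and censoring use different windows. An on-NA event after the last EOT date in its arm takes the Kaplan-Meier estimate to 100% where a coherent rule would give 0%, or 2.9% if all 33 others stay on NA and under observation, rising to 16.7% if only 5 do.

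Two broader readings should be avoided. First, not every follow-up event yields 100%: one in an early discontinuer while others are still before EOT gives about 3%. Second, 100% against 2.9% is not a general measure of the error, because 2.9% is the lowest comparator when follow-up events are kept, and the share remaining on NA is unknown.

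The effect is confined to the curves and medians of supporting analyses. The trial's efficacy conclusion and its main reporting of breakthrough and flares do not depend on them. It should be fixed because the rule gives a plainly misleading output and the repair is cheap, not because it threatens the trial.

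**What to change.** Preferred: add one sentence to each of SAP 5.4.1.3.4 and 5.4.1.3.5 saying that only events on or before EOT count in these endpoints. Report on-NA events in follow-up separately through the summaries already planned by arm and phase (SAP 5.4.2.1.13 and 5.4.2.1.14, read with the general rule in 5.4.2).

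Alternative: keep follow-up events, but count events and censor event-free participants within a single continuous on-treatment period, from first intake to the first stop of all study interventions including NA, with censoring at the last HBV DNA or ALT/AST assessment in that period. This has two costs that the SAP should state. Censoring then depends on meeting the NA completion criteria, which are based on ALT, HBV DNA, HBeAg and HBsAg, so it may be informative. It also leaves out NA re-treatment time, which SAP 5.4.1.1.13 counts as on-treatment.

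Either way the cost is one sentence in each section and a small programming change. No data collection changes.
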